7.2 Part D (Subjects With CF)

A schematic of the study design for Part D is shown in [Figure 7-1](#), which has a randomized, double-blind, placebo-controlled, parallel-group design. After completing the Screening Period, approximately 12 subjects will be randomized 3:1 to TC:placebo.

Screening in Part D will be initiated after the completion of Parts A, B, and C (cohorts needed for Part D dose selection only) through the Safety Follow-up Visit. The decision to proceed to Part D will be based on an evaluation of safety, tolerability, and PK data from completed cohorts in Parts A, B, and C. These data will be submitted to the IEC for approval before proceeding to screening for Part D. Refer to Section 9.3.2 of the protocol for additional details.

Figure 7-1 Schematic of Study Design for Part D

^a The planned VX-121 dose for Part D is 10 mg qd. This dose is predicted to provide an approximate AUC_{0-24h} of 10 µg·h/mL, which is within the predicted efficacious exposure range based on in vitro data. Based on emerging safety, tolerability, and PK data from Parts A, B, and C, the planned dose for Part D may be lowered to 5 mg qd. The total daily dose of VX-121 in Part D will be at least 1 dose level below the highest total daily dose tested in Part C. The dosage of TEZ/IVA in the TC will be TEZ 100 mg qd/IVA 150 mg q12h, which will be administered as TEZ 100 mg/IVA 150 mg FDC in the morning and IVA 150 mg in the evening.

7.3 Sample Size and Power

No formal sample size calculations have been performed. The number of subjects participating in each cohort of Parts A, B, and C is typical for first in human studies in healthy subjects and is considered sufficient to achieve the objectives of the study. Approximately 12 subjects in Part D is considered sufficient to meet the objectives of the study for this early assessment in subjects with CF.

7.4 Randomization

A randomization list for each part will be produced by Vertex Biostatistics or a qualified randomization vendor. The Vertex study biostatistician will review and approve the dummy randomization list. The final randomization list will be reviewed and approved by a designated unblinded biostatistician who is not a member of the study execution team (SET).

Parts A, B, and C

Subjects will be assigned a unique subject number (unique to subject and cohort). Only subjects who have completed screening assessments and are eligible for participation in the study will be randomized to receive active study drug or placebo during the Treatment Period. A list identifying subjects by their subject number will be maintained in the study file at the CRU.

Part D

Subjects will be assigned a unique subject number. Only subjects who have completed screening assessments and are eligible for participation in the study (and qualify to enter the Treatment Period) will be randomized to receive active study drug or placebo during the Treatment Period.

An interactive web response system (IWRS) will be used to assign subjects to treatment.

7.5 Replacement

Subjects who withdraw or are withdrawn before the first dose of study drug on the Day 1 Visit may be replaced.

Subjects who withdraw or are withdrawn for nonsafety reasons during the study drug treatment period(s) may be replaced at Vertex's discretion.

7.6 Blinding and Unblinding

Refer to the Section 10.7 of the protocol for details.

8 ANALYSIS SETS

8.1 All Subjects Set

For subjects other than those from Cohort A9, the **All Subjects Set** will include all subjects who were randomized or received at least 1 dose of study drug.

For subjects from Cohort A9, the All Subjects Set will include all subjects who were assigned a subject identification number or received at least 1 dose of study drug.

The All Subjects Set will be used for individual subject data listings, and the disposition summary table, unless specified otherwise.

8.2 Full Analysis Set (Part D Only)

The **Full Analysis Set** (FAS) will include all randomized subjects who carry the intended *CFTR* allele mutation and have received at least 1 dose of study drug in the Treatment Period. The FAS will be used for all PD and efficacy analyses in which subjects will be analyzed according to their randomized treatment group, unless otherwise specified.

8.3 Safety Set

The **Safety Set** will include all subjects who received at least 1 dose of study drug. All safety, demographics, baseline characteristics, study drug exposure, and concomitant medications will be summarized for the Safety Set.

9 STATISTICAL ANALYSIS

9.1 General Considerations

The Schedule of Assessments is provided in Section 3 of CSP. The precision standards for reporting safety and efficacy variables are provided in an internal Biometrics document that specifies the programming rules including the precision for derived variables.

Continuous data will be summarized using the following descriptive summary statistics: the number of subjects (n), mean, standard deviation (SD), median, minimum value (min), and maximum value (max).

Categorical data will be summarized using frequency counts and percentages. Percentages will be presented to 1 decimal place, unless otherwise specified.

Treatment-emergent (TE) Period

For subjects participating in Part A (excluding Cohorts A3 and A9), Parts B and C, the **TE Period** will be from the first dose date of study drug to (1) the Safety Follow-up Visit for subjects who have a Safety Follow-up Visit, or (2) 7 days after the last dose of study drug for subjects who do not have a Safety Follow-up Visit.

For subjects participating in Cohort A3 in Part A, 2 TE periods will be analyzed:

- **TE Period 1 (suspension [fed])** will begin from the administration of study drug on Day 1 (1) until the administration of VX-121 in fed state and with milk, or (2) the Safety Follow-up Visit for subjects who do not have the dose of VX-121 in fed state and with milk, and have a Safety Follow-up Visit, or (3) 7 days after the last dose of study drug for subjects who do not have the dose of VX-121 in fed state and with milk, and do not have a Safety Follow-up Visit.
- **TE Period 2 (suspension [fed and with milk])** will begin from the administration of study drug on Day 9 through the Safety Follow-up Visit or 7 days after the last dose of study drug, whichever comes first.

For subjects participating in Cohort A9 in Part A, 3 TE periods will be analyzed:

- **TE Period 1 (suspension [fed])** will begin from the administration of study drug on Day 1 (1) until the administration of VX-121 tablet in the fed state, or (2) the Safety Follow-up Visit for subjects who do not have the dose of VX-121 tablet in the fed state and have a Safety Follow-up Visit, or (3) 7 days after the last dose of study drug for subjects who do not have the dose of VX-121 tablet in the fed state and do not have a Safety Follow-up Visit.

- **TE Period 2 (tablet [fed])** will begin from administration of VX-121 tablet in the fed state (1) until the administration of VX-121 tablet in the fed state and with milk, or (2) the Safety Follow-up Visit for subjects who do not have the dose of VX-121 tablet in the fed state and with milk and have a Safety Follow-up Visit, or (3) 7 days after the last dose of study drug for subjects who do not have the dose of VX-121 tablet in the fed state and with milk, and do not have a Safety Follow-up Visit.
- **TE Period 3 (tablet [fed and with milk])** will begin from the administration of VX-121 tablet in fed state and with milk through the Safety Follow-up Visit or 7 days after the last dose of study drug for subjects who do not have a Safety Follow-up Visit..

For subjects participating in Part D, the **TE Period** will be from first dose date of study drug to Safety Follow-up Visit for subjects who have a safety follow-up visit; or 28 days after the last dose date of study drug for subjects who do not have a safety follow-up visit.

Treatment Groups

The Treatment Groups in Part A (excluding Cohorts A3 and A9), B, C and D will be defined as the corresponding VX-121 dose groups.

The 2 Treatment Groups in Cohort A3 will correspond to suspension [fed] and suspension [fed and with milk] respectively.

The 3 Treatment Groups in Cohort A9 will correspond to suspension [fed], tablet [fed] and tablet [fed and with milk] respectively.

Baseline value

The baseline value will be defined as the most recent non-missing measurement (scheduled or unscheduled) collected before the first dose of study drug. If a pre-dose measurement is missing and no drug-free unscheduled assessments are performed before the first dose of the study, the baseline will be missing. For ECG, the baseline value will be defined as the most recent non-missing measurement (or the average of triplicate measurements, if the most recent non-missing measurements are obtained in triplicate), before the first dose of study drug of the Treatment Period.

Absolute change from baseline will be calculated as post-baseline value – baseline value.

Relative change from baseline will be calculated as (post-baseline value – baseline value)/baseline value.

Visit Window: For Parts A, B and C, the majority of assessments are predicted to be on schedule. Visit windows will not add significant value to the analysis and will not be applied. For Part D, the analysis visit windows for protocol-defined visits are provided in [Appendix A](#).

Unscheduled visits: Unscheduled visit measurements will be included in analysis as follows:

- 1) In scheduled visit windows per specified visit windowing rules
- 2) In the derivation of baseline and last on-treatment measurements
- 3) In the derivation of maximum and minimum values during TE period, and maximum and minimum change from baseline values during TE period for safety analyses
- 4) In individual subject data listings as appropriate.

Incomplete/missing data (e.g., dates, post-baseline values) will not be imputed, unless otherwise specified; i.e., all missing values and missing post-baseline values will remain as missing in all statistical analyses and listings, unless otherwise specified.

Outliers: No formal statistical analyses will be performed to detect and/or remedy the presence of statistical outliers.

All subject level data, including those derived, will be presented in the individual subject data listings; listings will be based on the All Subjects Set.

Unless otherwise specified, the analyses will be presented by treatment group/treatment sequence. Separate summary tables will be produced for each part. The number of cohorts and the dose levels of each cohort are subject to change to reflect the actual cohorts enrolled and dose levels.

The treatment group and treatment sequence for all cohorts in each part will be labeled as follows.

- Part A (Cohorts A1, A2 and A4 through A6, or A7, A8 when applicable): Placebo, VX-121 10 mg, VX-121 20 mg, VX-121 40 mg, VX-121 60 mg, VX-121 90 mg and VX-121 Total.
- Part A (Cohort A3): Placebo and VX-121 5 mg within the sequence of Placebo -> VX-121 (fed with milk) ; VX-121 5 mg and VX-121 5 mg [fed with milk] within the sequence of VX-121 5 mg -> VX-121 5 mg (fed with milk) , and VX-121 Total.
- Part A (Cohort A9): VX-121 10 mg suspension [fed], VX-121 10 mg tablet [fed], and VX-121 10 mg tablet [fed with milk]
- Part B: Placebo, VX-121 10 mg qd, VX-121 20 mg qd, VX-121 40 mg qd, VX-121 60 mg qd, and VX-121 Total

- Part C: Triple Placebo, VX-121 10 mg qd + TEZ 100 mg qd/IVA 150 mg q12h, and VX-121 20 mg qd+ TEZ 100 mg qd/IVA 150 mg q12h, and VX-121 Total when there are more than one TC doses.

- Part D: Triple Placebo, and VX-121 TBD mg + TEZ 100 mg qd/IVA 150 mg q12h.

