**Parts C and D**

Active substance: VX-121  
Activity: CFTR corrector  
Strength and route of administration:  
Suspension: Drug substance will be reconstituted at various concentrations for oral administration  
Tablet: 5-mg tablet for oral administration

Active substance: TEZ (VX-661) and IVA (VX-770)  
Activity: CFTR corrector and potentiator ( $\text{Cl}^-$  secretion)  
Strength and route of administration: 100-mg TEZ/150-mg IVA, film-coated fixed-dose combination (FDC) tablet for oral administration

Active substance: IVA (VX-770)  
Activity: CFTR potentiator  
Strength and route of administration: 150-mg film-coated tablet for oral administration

**Study Duration** Excluding the Screening Period, the study duration for each subject is 9 to 12 days for Cohorts A1, A2, A4, A5, and A6, 18 to 20 days for Cohort A3, 26 to 28 days for Cohort A9, 18 to 21 days for Part B, 22 to 25 days for Part C, and

approximately 7 to 9 weeks for Part D.

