a On dosing days, assessments will be performed before dosing, unless noted otherwise.b Additional PK samples and safety assessments may also be performed at the discretion of the investigator. See [Section 9.1.1.4](#) for details.c Subjects will be discharged from the CRU on Day 16 after completion of the study visit assessments.d Weight will be measured with shoes off.e Standard 12-lead ECGs will be performed in the supine position after the subject has been at rest for at least 5 minutes. The ECG will be done before any other procedures that may affect heart rate, such as blood draws. On Days 1 and 9, ECGs will be collected before dosing and approximately 1, 3, 5, and 6 hours ( $\pm$  15 min) after dosing.f Vital signs will be performed after the subject has been at rest for at least 5 minutes.g Blood samples for PK assessments will be collected on Days 1 and 9 before dosing (0 hours), and at 1, 1.5, 2, 3, 4, 5, 6, 8, 12, 24 (Days 2, 10), 36 (Days 2, 10), 48 (Days 3, 11), 72 (Days 4, 12), 96 (Days 5, 13), 120 (Days 6, 14), 144 (Days 7, 15), and 168 (Days 8, 16) hours after dosing. Acceptable PK sampling windows are provided in [Table 11-1](#). At the Safety Follow-up Visit, a single blood sample for PK analysis will be collected.h Subjects will be randomized 3:1 to receive VX-121 or placebo. Study drug will be administered in the fed state ([Section 9.6.1](#)).i All subjects will receive open-label VX-121. Study drug will be administered in the fed state and with milk ([Section 9.6.1](#)).j All medications taken from 28 days before the first dose of study drug through the end of the study will be recorded.

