#### **9.1.1.3 Follow-up**

Subjects will have a Safety Follow-up Visit 7 to 10 days after the last study drug dose. Safety Follow-up Visit assessments are listed in [Table 3-2](#) (Cohorts A1 through A6 [up to A8]), [Table 3-3](#) (Cohort A3), [Table 3-4](#) (Cohort A9), [Table 3-5](#) (Part B), and [Table 3-6](#) (Part C).

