### **12.3.1 General Considerations**

Only descriptive analyses will be performed; no statistical hypothesis testing will be done. Continuous variables will be summarized using the following descriptive summary statistics: the number of subjects (n), mean, SD, SE, median, minimum value, and maximum value. Categorical variables will be summarized using counts and percentages.

All individual subject data for subjects who were randomized or received at least 1 dose of study drug will be presented in individual subject data listings.

For Parts A, B, and C, the **Treatment-emergent (TE) Period** will be from the first dose date of study drug to (1) the Safety Follow-up Visit for subjects who have a Safety Follow-up Visit, or (2) 7 days after the last dose of study drug for subjects who do not have a Safety Follow-up Visit.

For Part D, the **TE Period** will be from first dose date of study drug to 28 days after the last dose date of study drug.

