9.4.1 Adverse Events

AEs will be coded according to MedDRA (Version 20.1 or above). The number and percentage of subjects experiencing an AE will be summarized by the MedDRA System Organ Class (SOC) and Preferred Term (PT). AEs will be classified as pretreatment or treatment-emergent.

Pretreatment AEs are defined as AEs that were reported or worsened (either in severity or seriousness) after signing the ICF up to the start of study drug dosing.

Treatment-emergent adverse events (TEAEs) for all cohorts except Cohorts A3 and A9 are defined as any AE that worsened (either in severity or seriousness) or that was newly developed at or after the first dose date of study drug during the Treatment Period through the end of the TE Period for the Treatment Period.

For Cohort A3 and A9, TEAEs will be assigned to each treatment group based on the start date of the AE and the start of study drug administration dates within the corresponding TE Period.

For AEs with completely missing or partially missing start dates, if there is no clear evidence that the AEs started before or after study treatment, the AEs will be classified as TEAEs corresponding to the Treatment Period. Unless otherwise specified, TEAE refers to TEAE during the Treatment Period.

Details for imputing missing or partial start dates of adverse events are described in [Appendix C](#), which is applicable to Part D only.

AE summary tables will be presented for TEAEs only and will include the following: (1) Overview of TEAEs (2) all TEAE; (3) related (defined as possibly related, related, or missing) TEAEs; (4) serious TEAEs; (5) TEAEs by severity; (6) TEAEs by relationship; and (7) TEAEs leading to treatment discontinuation.

Summaries will be presented using frequency counts and percentages by treatment group/treatment sequence for each part (i.e., number and percentage of subjects with an event); for the summary table of TEAE Overview, an additional column of overall will be provided.

When summarizing the number and percentages of subjects, subjects with multiple occurrences of the same adverse event will be counted once, and only the maximum severity level will be presented in the severity summaries, and the strongest relationship level in the relationship summaries.

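### The SAP closes Cohort A3's milk-dose treatment-emergent period at 7 days even when the subject has a later follow-up visit, contrary to the protocol

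*SAP*

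**What the plan says.** Protocol 12.3.1 sets one rule for Parts A, B and C and makes no exception for Cohort A3. The treatment-emergent (TE) period runs from the first dose to "the Safety Follow-up Visit for subjects who have a Safety Follow-up Visit, or (2) 7 days after the last dose" for subjects who have no such visit.

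SAP 9.1 repeats that rule for the other Part A cohorts and for Parts B and C. Cohorts A3 and A9 are split into periods by dosing occasion. If the milk dose is not given, A3 TE Period 1 runs to "the Safety Follow-up Visit for subjects who do not have the dose of VX-121 in fed state and with milk" and who attend that visit. The last period of Cohort A9, TE Period 3, ends at follow-up, or "7 days after the last dose of study drug for subjects who do not have a Safety Follow-up Visit". Only A3 TE Period 2 runs "through the Safety Follow-up Visit or 7 days after the last dose of study drug, whichever comes first".

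Two SAP sections make the end of the period matter:

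- **Section 9.4.1:** A3 and A9 events are assigned to treatment groups by start date within the corresponding TE period, and "AE summary tables will be presented for TEAEs only and will include the following" the severity, relationship and seriousness tables.
- **Section 9.4.3:** the descriptive ECG summaries and the maximum QT/QTc categories are both limited to the TE period.

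**The concern.** The SAP departs from the protocol's definition for one period in one cohort and does not say why. Because the follow-up visit cannot come before day +7 if it is in window, taking the earlier date means that the visit never sets the end of the period.

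The SAP's rules then have these consequences:

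- An adverse event that starts after the 7-day point but before follow-up belongs to no A3 treatment group. It is absent from every AE summary table.
- The ECG scheduled at the follow-up visit is excluded from the TE-limited ECG tables when the visit is after day +7.
- The cohort is handled unevenly. A subject who misses the milk dose is treatment-emergent through follow-up; a subject who takes it is cut off at 7 days.
- With 3:1 randomization of about 8 subjects, about 2 received placebo first. Their only active dose falls in the shortened period.

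Safety is the primary endpoint, so A3 TEAE counts and QT/QTc maxima after the milk dose could be understated. That would happen only if an event starts, or the largest value occurs, between Day 16 and the follow-up visit.

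**Working it through.** **Inputs**

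- Milk dose, the last dose in A3: Day 9 (protocol 9.6.1, Cohort A3, and Table 3-3).
- Follow-up timing: "Subjects will have a Safety Follow-up Visit 7 to 10 days after the last study drug dose" (protocol 9.1.1.3).
- End of the inpatient stay: "Subjects will be discharged from the CRU on Day 16 after completion of the study visit assessments" (protocol Table 3-3). Day 16 is Day 9 + 7, and the follow-up is marked as a separate outpatient visit.
- Stated durations: "18 to 20 days for Cohort A3, 26 to 28 days for Cohort A9, 18 to 21 days for Part B" (protocol synopsis). The synopsis also gives 9 to 12 days for A1 and similar cohorts, and 22 to 25 for Part C.

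**Step 1. Reproduce the stated durations, to see when the A3 follow-up is planned.** Count Day -1 plus Day 1 through the follow-up day, with no Day 0: duration = last dose day + offset + 1.

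| Cohort or part | Last dose | Computed for +7 to +10 | Stated | Offset implied |
|---|---|---|---|---|
| A1 etc. | Day 1 | 9 to 12 | 9 to 12 | +7 to +10 |
| Part B | Day 10 | 18 to 21 | 18 to 21 | +7 to +10 |
| Part C | Day 14 | 22 to 25 | 22 to 25 | +7 to +10 |
| A3 | Day 9 | 17 to 20 | 18 to 20 | +8 to +10 |
| A9 | Day 17 | 25 to 28 | 26 to 28 | +8 to +10 |

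The count reproduces three stated ranges exactly. For A3 and A9 the stated range matches a follow-up at +8 to +10, which fits discharge on day +7 followed by a separate visit.

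**Step 2. End of A3 TE Period 2 under each rule.** SAP: Day 9 + min(offset, 7). Protocol: Day 9 + offset.

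| Follow-up | SAP end | Protocol end | Days lost | Share of dose-to-follow-up interval | Follow-up ECG in SAP period |
|---|---|---|---|---|---|
| +7 (Day 16) | Day 16 | Day 16 | 0 | 0 | yes |
| +8 (Day 17) | Day 16 | Day 17 | 1 | 1/8 = 12.5% | no |
| +9 (Day 18) | Day 16 | Day 18 | 2 | 2/9 = 22.2% | no |
| +10 (Day 19) | Day 16 | Day 19 | 3 | 3/10 = 30% | no |

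**Step 3. Cohort total.** Across 8 subjects the loss is 8 × 0 = 0 to 8 × 3 = 24 subject-days. If all visits fall at +8 to +10, it is 8 × 1 = 8 to 24.

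**Step 4. Which outputs change.** AE tables, TE-period ECG summaries and QT/QTc maxima are affected. Outside Part D, laboratory and vital-sign summaries are by scheduled time point with no TE limit, so they are not. AE collection is unchanged, and SAP 9.4.1 still lists all events through follow-up.

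**The case against.** The wording conflict is not in dispute; its importance is. The strongest points are these:

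- **QT/QTc.** Protocol 12.3.4.3 speaks of maximum on-treatment values, a term it does not define. An ECG 8 to 10 days after a single dose is only arguably on treatment, so leaving it out may not breach the protocol. This stands for the protocol comparison. It does not bring the ECG back, because SAP 9.4.3 ties the maxima to the TE period.
- **Descriptive ECG summary.** Follow-up is a scheduled time point, so the SAP could be read as including it. The same SAP sentence limits the summary to the TE period, so the text as written excludes it.
- **ECGs retained.** The Day 9 post-dose ECGs at about 1, 3, 5 and 6 hours stay inside the period. So, as far as the columns of Table 3-3 can be read, does one on the day of discharge. This limits what can be missed.
- **Timing.** The +8 to +10 schedule is inferred from the durations; the stated window is 7 to 10 days. The secure range is therefore 0 to 24 subject-days.
- **Denominator.** Measured from Day 1, the loss is 1/16 (6%) at +8 to 3/18 (17%) at +10, smaller than the shares shown above.
- **Reach.** One cohort at 5 mg, the lowest planned Part A dose, is affected. There is no safety hypothesis test, and dose escalation rests on ongoing review rather than on these tables.

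These points make the effect small. None explains the exception or removes the conflict.

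**Conclusion.** The concern holds. The A3 TE Period 2 rule contradicts protocol 12.3.1 and differs from every other TE period that the SAP defines for Parts A, B and C, including its direct counterpart in A9. Followed as written, it closes the period on Day 16 for every in-window visit. Events starting after that day leave the TEAE tables, and a follow-up ECG at +8 to +10 leaves the ECG and QT/QTc tables.

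The size is modest: about 8 subjects, 0 to 3 days each, and at most one follow-up ECG per subject. The effect is confined to descriptive summaries. Whether any count changes depends on whether an event or an extreme value falls in those days, which the documents cannot tell us.

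The day counts assume the milk dose is given on Day 9, the visit is in window, and days are calendar days with the last day included. The lower bound of 8 subject-days also assumes the visit timing inferred from the stated durations; without that it is 0. The change should be made because it affects the primary endpoint and corrects an unexplained departure from the protocol.

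**What to change.** In SAP 9.1, Cohort A3 TE Period 2, remove the earlier-of-two-dates condition and use the A9 TE Period 3 rule: the period ends at the Safety Follow-up Visit, or "7 days after the last dose of study drug for subjects who do not have a Safety Follow-up Visit". If the exception was intended, the SAP should say so and justify it.

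The cost is one phrase in the SAP, with no new data and no protocol change. A3 TEAE counts and QT/QTc maxima would stay the same or rise slightly.

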Approximately 8 subjects per cohort, randomized 3:1 (VX-121:placebo) except for Cohort A9

Cohort A9 (Approximately 8 subjects, open-label VX-121, single sequence)^b

Part B: Multiple-dose escalation of VX-121

Approximately 8 subjects per cohort, randomized 3:1 (VX-121:placebo)

[figure not shown]

Table 7-1 Study Design for Parts A, B, and C

Part C: Multiple-dose escalation of VX-121 in TC with TEZ/IVA^c		
Approximately 8 subjects per cohort, randomized 3:1 (VX-121/TEZ/IVA:triple placebo)		
Planned Dosage (qd, 14 days)		
Cohort C1	10 mg qd	
Cohort C2		20 mg qd

Notes: In Part A, planned doses are shown; any cohort may be initiated at a lower or higher dose level than the planned dose based on emerging safety, tolerability, and PK data. No dose increment will be expected to yield greater than a 3-fold increase (Cohorts A1 through A3) or a 2-fold increase (all other Part A cohorts and Part B cohorts) in exposure from the preceding dose level. Dose escalation criteria and predefined stopping criteria are described in Section 9.7.1 and Section 9.8.1 of the protocol.

^a In addition to randomized study drug administration depicted above, after a washout of at least 8 days all subjects will receive an additional 5 mg single dose of open-label VX-121 suspension with milk to evaluate the effect of milk on VX-121 exposure.

^b Subjects will receive a single dose of VX-121 on 3 dosing occasions with at least an 8-day washout between dosing occasions. VX-121 doses include a single oral dose of suspension, a single oral dose of tablet to evaluate the relative BA of the tablet, and a single oral dose of tablet with milk to evaluate the effect of milk on VX-121 exposure (the planned dose is 10 mg for both formulations, but it will not exceed the highest dose that was safe and well tolerated in a previous Part A cohort).

[figure not shown]
^c The dosage of TEZ/IVA will be TEZ 100 mg qd/IVA 150 mg q12h, which will be administered as TEZ 100-mg/IVA 150-mg FDC in the morning and IVA 150 mg in the evening.

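### SAP 9.1 groups Cohort A3 in two conflicting ways: one does not separate placebo from VX-121 in Period 1, and the other uses one label for both the milk and the no-milk dose

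*SAP*

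**What the plan says.** **Design.** SAP Table 7-1 describes the Part A cohorts as follows: "Approximately 8 subjects per cohort, randomized 3:1 (VX-121:placebo) except for Cohort A9". Protocol Table 3-3, footnote h, repeats the ratio for Day 1 of Cohort A3: "Subjects will be randomized 3:1 to receive VX-121 or placebo". In the second period, per the footnote to SAP Table 7-1, "after a washout of at least 8 days all subjects will receive an additional 5 mg single dose of open-label VX-121 suspension with milk". The schedule puts that dose on Day 9.

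**Group definition (SAP 9.1, Treatment Groups).** The general rule leaves A3 out: "The Treatment Groups in Part A (excluding Cohorts A3 and A9), B, C and D will be defined as the corresponding VX-121 dose groups". A3 has its own rule: "The 2 Treatment Groups in Cohort A3 will correspond to suspension [fed] and suspension [fed and with milk] respectively".

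**Adverse-event rule (SAP 9.4.1).** "For Cohort A3 and A9, TEAEs will be assigned to each treatment group based on the start date of the AE", together with the dosing dates within each treatment-emergent period. The rule does not mention randomised arm. The same section says that summaries are shown by treatment group or treatment sequence.

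**Label list (later in SAP 9.1).** For the placebo-first sequence of A3 the labels are "Placebo and VX-121 5 mg within the sequence of Placebo -> VX-121 (fed with milk"). For the active-first sequence they are VX-121 5 mg and VX-121 5 mg [fed with milk]. A VX-121 Total follows. The other single-dose cohorts have a separate block that begins "Part A (Cohorts A1, A2 and A4 through A6, or A7, A8 when applicable): Placebo, VX-121 10 mg, VX-121 20 mg" and continues to 90 mg and a total. It has no 5 mg column.

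**The concern.** Safety is the primary objective, and the adverse-event tables are its main output. The A3 groups are named by formulation and feeding condition. In A9, where every subject receives VX-121, that is sufficient. In A3, Period 1 is a randomised comparison in which both arms take a suspension in the fed state, so the name suspension [fed] describes the placebo subjects equally well. A programmer who builds the A3 table from the group definition and the date rule has no instruction to split the arms.

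A programmer who works from the label list will split them, but then meets one label with two meanings. If columns are combined by label across sequences, milk and no-milk doses are mixed in the cohort that was designed to tell them apart.

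There is also a smaller question of presentation. The protocol synopsis counts A3, at 5 mg, among the single-dose escalation cohorts A1 through A6, yet the single-dose block of tables omits it.

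**Working it through.** **Inputs.** About 8 subjects per cohort, 3:1 randomisation, and 7 planned Part A cohorts of which A9 is open-label (Protocol synopsis; SAP Table 7-1).

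**The plan's own figures.** Part A: 7 × 8 = 56. Study: 56 + 6 × 8 + 2 × 8 + 12 = 132. Both match the synopsis.

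**Step 1: does the name suspension [fed] cover placebo?**
- The protocol synopsis gives VX-121 or placebo as a suspension under fed conditions.
- Protocol Section 10 counts the matching placebos as study drug.
- SAP 9.1 gives A3's first treatment-emergent period the same name, suspension [fed], and starts it at the Day 1 administration of study drug.

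Nothing in the group definition or the date rule therefore excludes a placebo subject.

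**Step 2: size if the definition is followed alone.**
- VX-121: 8 × 3/4 = 6. Placebo: 8 × 1/4 = 2. Placebo share of the group: 2/8 = 25%.
- Pooled rate = (6 × VX-121 rate + 2 × placebo rate) / 8.

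| Illustrative events | VX-121 rate | Rate shown if pooled |
|---|---|---|
| 3 of 6 VX-121, 0 of 2 placebo | 50% | 3/8 = 37.5% |
| 0 of 6 VX-121, 1 of 2 placebo | 0% | 1/8 = 12.5% |

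**Step 3: the label list.**

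| Sequence | Period 1 label | Period 2 label | Actual Period 2 dose |
|---|---|---|---|
| Placebo first (n=2) | Placebo | VX-121 5 mg | 5 mg with milk |
| VX-121 first (n=6) | VX-121 5 mg | VX-121 5 mg [fed with milk] | 5 mg with milk |

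Combined by label, VX-121 5 mg would hold 2 milk-dose and 6 no-milk subjects, and the milk column would hold 6 subjects instead of 6 + 2 = 8.

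**Step 4: the single-dose block.**
- Without A3: 5 × 6 = 30 VX-121 and 5 × 2 = 10 placebo.
- With A3 Period 1: 6 × 6 = 36 and 6 × 2 = 12.
- Share outside the block: 6/36 = 17% of VX-121 and 2/12 = 17% of placebo, including the lowest planned dose.

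**The case against.** The best defence is to read SAP 9.1 as a whole. Two dosing conditions crossed with two randomised sequences give exactly the four labelled columns, and Placebo is one of them. SAP 9.4.1 allows presentation by sequence, and sequence separates the arms. The group definition names placebo for no cohort, yet the label list supplies it for all the randomised ones. The missing milk tag can be recovered from the sequence heading.

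Much of this stands. A reader might infer from the group definition that the A3 safety table will have no placebo control. The documents do not support that, because the label list gives A3 a Placebo column.

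What does not stand is the parallel with the other cohorts. There the groups are VX-121 dose groups, which cannot take in a placebo subject. A3's groups are dosing conditions, which can. The crossed reading is sensible, but it is not written down, and the event rule refers to treatment group and dates.

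A reader might also infer that A3's Period 1 data are lost from the safety evaluation. They are not: A3 has its own block and its own listings. No text requires A3 to sit with the other cohorts, and separate display has reasons: a different assessment schedule, a second open-label dose, and a Period 1 that ends at that dose. Nor does the omission support an argument from confidence bounds on unseen events. No planned analysis uses them, and they would assume one event rate from 5 to 90 mg and independent subjects, although a subject may enrol in two Part A cohorts.

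**Conclusion.** The inconsistency is real and should be resolved. The group definition and the event rule do not separate 2 placebo from 6 VX-121 subjects in A3 Period 1. The label list does, but gives the milk and no-milk doses the same name. Pooling is one of two conflicting readings, so the 25% placebo share is what would follow from the definition taken alone, not a description of what the tables will certainly show.

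Leaving 5 mg out of the single-dose block is a weakness of presentation. It matters somewhat because Part A's primary objective is the safety of single ascending doses, and because the protocol names 5 mg qd as the possible lower dose for Part D.

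All counts assume 8 subjects per cohort, an exact 3:1 split, no replacements and no Cohorts A7 or A8. They count cohort places, since one person may fill two. The event rates are illustrations, not predictions.

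**What to change.** 1. In SAP 9.1, replace the A3 sentence with three groups: Placebo [fed] (Period 1, planned n=2), VX-121 5 mg [fed] (Period 1, planned n=6) and VX-121 5 mg [fed with milk] (Period 2, planned n=8, shown by sequence).
2. In the label list, change the placebo sequence's second label to VX-121 5 mg [fed with milk], and write the active sequence's first label as VX-121 5 mg [fed].
3. In SAP 9.4.1, state that A3 events are assigned by randomised arm and treatment-emergent period.
4. As an inexpensive improvement, add A3 Period 1 as a 5 mg column beside the other single-dose cohorts, with its 2 placebo subjects in pooled Placebo. Footnote that Period 1 ends at the Day 9 dose, whereas the other cohorts are followed to the Safety Follow-up Visit 7 to 10 days after dosing. Keep A3's own block.

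The cost is SAP wording and table shells. No new data, analysis or change in conduct is needed, and SAP Section 4 provides for amendment before database lock. The one drawback is the slightly different observation period in item 4, which the footnote covers.
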